4.10 RATIONALE FOR UNILATERAL ADMINISTRATION

In this study the contralateral non-administered eye will act as the control (ie, intra patient control) as well as the untreated areas of the study eye. The more severely affected of the two eyes will be injected. This is done with the intention of minimizing risk to the less affected eye and thus reducing risk to the patient's remaining vision.

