6.2 SECONDARY ENDPOINTS

The primary time points will be considered the 6- and 12-month visits.

To determine a delay in retinal degeneration following subretinal injection of SAR421869 through changes in function relative to the untreated contralateral eye utilizing the following retinal analytical techniques:

- Best-corrected visual acuity (BCVA).
- Contrast sensitivity.
- Indirect ophthalmoscopy.
- Visual function questionnaire VFQ-25/ CVAQC (when possible).
- Full dilated slit-lamp examination.
- Fundus photography – Panretinal photomontage.

- Visual field testing: Semi-automated Kinetic Perimetry (SKP) and Full-Field German Adaptive Thresholds Estimation (GATE) Static Perimetry, and microperimetry.
- Autofluorescence.
- Electroretinogram (ERG).
- Optical coherence tomography (OCT).

Adverse Events

The number and severity of any adverse events associated with SAR421869 administration will be assessed at each time point.

Immunology Endpoint

Humoral antibody response to SAR421869 administration.

Clinical Laboratory Tests

Hematology, biochemistry, urinalysis and other laboratory data will be measured at various time points throughout the study. Values will be flagged as High or Low if outside the laboratory normal range. Out of range values will be assessed as clinically significant (CS) or not clinically significant (NCS) by the investigator. CS out of range values will be recorded as adverse events. Blood for immunology and blood for PCR will also be taken at multiple time points throughout the study, as will urine samples for biodistribution assessment.

Biodistribution Endpoint

SAR421869 distribution in blood and urine will be assessed by polymerase chain reaction (PCR).

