7.4 Secondary Endpoints

The secondary endpoints include changes in the study eye from Day -28 to Weeks 24 and 48 in function relative to the untreated, contralateral eye in several visual function measures. The primary endpoints of BCVA, ocular inflammation and OCT will also serve as secondary endpoint measures. Analysis of these parameters will be conducted as outlined in [Sections 7.3.2, 7.3.3](#) and [7.3.5](#), respectively.

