7.4.2 Electroretinogram (ERG)

Full-field ERG responses include 30 Hz flicker; photopic single flash a- and b-waves; scotopic cone-rod flash a- and b-waves; and scotopic rod, dim white light b-wave. Amplitudes and implicit times will be presented in tabular format and graphically by patient and cohort for study eye and fellow eye as appropriate. Mean changes from baseline will also be summarized. Clinically significant changes, defined as a decrease in ERG amplitude of greater than 50%, from Day -28 ERG data will be indicated and listed where appropriate.

Peak amplitudes (nV/deg²) and latency (ms) values for multifocal ERG (mfERG) responses at Day -28 will be tabulated for each of six concentric rings in the visual field by patient and eye. The concentric ring minimum and maximum are collected separately. The minimum and maximum are summed together to obtain the peak amplitude (nV/deg²). To examine change

in mfERG responses in the central visual field across visits, the mean changes from Day -28 across the peak amplitudes and latencies of inner rings (Rings 1-3) will be tabulated and plotted against time by cohort, patient and eye. In addition, mean changes across the peak amplitude and latencies of outer rings (Rings 4-6) will also be tabulated and plotted by cohort, patient and eye against time.

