8.3.2 BCVA, Ocular Inflammation and IOP

Table 3L lists the primary outcomes of BCVA, ocular inflammation and IOP for the study and fellow eyes by patient and visit, Tables 3M and 3N summarize mean changes in BCVA and IOP, respectively, by cohort and visit for the study and fellow eyes and Table 3O summarizes the number and percentage of individuals with elevated (≥ 25 , ≥ 30 and ≥ 35 mmHg) IOP in the study eye. Changes in ophthalmic inflammation by dose group, visit and eye will also be summarized in Table 3P. Ophthalmic outcome data will be displayed graphically in plots similar to Figures 3Q and 3R. Tables and plots will be given for the study eye as well as for the fellow eye, and labeled appropriately.

Table 3L: Ophthalmic Outcome Listing for Study Eye and Fellow Eye by Patient and Visit

Patient ID	Visit	Study	IOP		BCVA		Anterior Cells		Anterior Flare		Vitreous Cells		Vitreous Haze		Macular Edema	
			Fellow	Study	Study	Fellow	Study	Fellow	Study	Fellow	Study	Fellow	Study	Fellow	Study	Fellow

Table 3M: Mean Changes from Pre-surgical BCVA by Cohort and Visit

Cohort	Visit	Study Eye					Fellow Eye				
		N	Mean	Std	Min	Max	N	Mean	Std	Min	Max

Table 3N: Mean Changes from Pre-surgical IOP by Cohort and Visit

[figure not shown]
Cohort	Visit	Study Eye					Fellow Eye				
		N	Mean	Std	Min	Max	N	Mean	Std	Min	Max

Table 3O: Patients Experiencing Elevated IOP in the Study Eye Following Treatment by Cohort

Cohort	IOP ≥ 25 mmHg				IOP ≥ 30 mmHg				IOP ≥ 35 mmHg			
	No		Yes		No		Yes		No		Yes	
	N	%	N	%	N	%	N	%	N	%	N	%
1												
2												
3												
4												
5												
All												

[figure not shown]
Table 3P: Changes in Ophthalmic Inflammation in the Study Eye by Cohort and Visit

Cohort	Visit	Anterior Chamber Cells		Anterior Chamber Flare		Vitreous Cells				Vitreous Haze			
		No Change	Half-Step Increase	No Change	1-Step Increase	Half-Step Decrease	No Change	Half-Step Increase	2-Step Decrease	1-Step Decrease	No Change	Half-Step Increase	
		N	%	N	%	N	%	N	%	N	%	N	%

Figure 3Q: Ophthalmic Outcomes Over Time (Days from Surgery) by Patient

Mean changes from Baseline (Day -28) will be plotted for ophthalmic outcomes versus dose cohort in a plot similar to Figure 3R.

Figure 3R: Mean Change in Ophthalmic Outcome from Baseline by Dose Cohort

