8.4.2 ERG

Table 4C lists full field ERG response amplitudes (microvolts) and implicit times (ms) parameters by patient and visit for the study eye. Fellow eye data will be summarized similarly. The a- and b- wave amplitudes and implicit times may be represented graphically, similar to Figure 4D by patient and cohort as appropriate. Mean change in full field ERG will also be summarized. Clinically significant changes from Day -28 in ERG data will be indicated and listed where appropriate.

Table 4C: Full Field ERG Response (Study Eye) Amplitude and Implicit Time Data by Cohort, Patient and Visit

Cohort	Patient ID	Visit	30 Hz Flicker		Photopic Single Flash (a-wave)		Photopic Single Flash (b-wave)		Scotopic Cone-Rod (a-wave)		Scotopic Cone-Rod (b-wave)		Scotopic Rod (dim, b-wave)	
			Amplitude	Implicit Time	Amplitude	Implicit Time	Amplitude	Implicit Time	Amplitude	Implicit Time	Amplitude	Implicit Time	Amplitude	Implicit Time

Figure 4D: Full Field ERG Data Over Time

Tables 4E, 4F and 4G list the mean peak amplitude and latencies for each patient at Day -28 for each ring, mean changes in these values for the central (Rings 1-3) visual field and mean changes for the peripheral (Rings 4-6) visual field, respectively. Figures 4H and 4I illustrate the change in peak and latency values for the central and peripheral visual fields, respectively, against time for each patient.

Table 4E: Mean Peak Amplitudes and Latencies at Baseline (mfERG) by Cohort and Patient

Cohort	Patient ID	Study Eye	Ring 1		Ring 2		Ring 3		Ring 4		Ring 5		Ring 6	
			OD	OS										

Table 4F: Central Field (Rings 1-3) Summary mfERG Data by Cohort and Patient

Cohort	Patient ID	Study Eye	Mean Central Field (Baseline)		Mean Change (Week 24)		Mean Change (Week 48)	
			OD	OS	OD	OS	OD	OS

Table 4G: Peripheral Field (Rings 4-6) Summary mfERG Data by Cohort and Patient

Cohort	Patient ID	Study Eye	Mean Peripheral Field (Baseline)		Mean Change (Week 24)		Mean Change (Week 48)	
			OD	OS	OD	OS	OD	OS

[figure not shown]
[figure not shown]
Figure 4H: Change in Central Field (Rings 1-3) mfERG Response Over Time

Figure 4I: Change in Peripheral Field (Rings 4-6) mfERG Response Over Time

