- [Table 3M](#): Mean Changes from Pre-surgical BCVA by Cohort and Visit
- [Table 3N](#): Mean Changes from Pre-surgical IOP by Cohort and Visit

- Table 3O: Patients Experiencing BCVA Change in the Study Eye at Week 48 Following Treatment by Cohort
- Table 3P: Patients Experiencing Elevated IOP in the Study Eye at Week 48 Following Treatment by Cohort
- **Tables 3Q-3S:** Changes in Ophthalmic Inflammation in the Study Eye by Cohort and Visit
- Figures 3T-3V: BCVA in Study and Fellow Eyes by Patient in Cohort X
- Figures 3W-3Y: IOP in Study and Fellow Eyes by Patient in Cohort X
- Figure 3Z: Mean Changes in BCVA in the Study Eye over Time by Cohort
- Figure 3AA: Mean Changes in IOP in the Study Eye over Time by Cohort
- **Listing 3BB:** Listing of Patients with Abnormal and/or Clinically Significant Labs
- Listing CC: Abnormal Physical Examination Listing by Patient
- **Table 3DD:** Mean Change in Continuous Laboratory Parameters by Cohort and Visit
- **Listing 3EE:** OCT Listing by Patient and Visit
- Figures 3FF-3HH: Central Retinal Thickness (OCT) for Study and Fellow Eyes in Cohort X
- Figures 3II-3KK: Macular Volume (OCT) for Study and Fellow Eyes in Cohort X
- Table 3LL: Change from Baseline in Vital Signs by Cohort and Visit
- **Listing 4A:** Static (GATE) Perimetry Data by Patient
- Figures 4B-4D: Volume of Full Field Hill of Vision Measured by Static (GATE) Perimetry by Patient in Cohort X
- Figures 4E-4G: 111pt grid-Volume of Full Field Hill of Vision Measured by Static (GATE) Perimetry by Patient in Cohort X
- **Listing 4H:** Kinetic (SKP) Perimetry Data by Patient
- Figures 4I-4K: SKP Data in Study Eyes by Patient in Cohort X
- **Listing 4L:** Full Field ERG Response (Study Eye) Amplitude and Implicit Time Data by Cohort, Patient and Visit
- **Table 4M:** Mean Peak Amplitudes and Latencies at Baseline (mfERG) by Cohort and Patient
- **Table 4N:** Central Field (Rings 1-3) Summary mfERG Data by Cohort and Patient
- **Table 4O:** Peripheral Field (Rings 4-6) Summary mfERG Data by Cohort and Patient
- Listing 5A: Detailed Listing of Immunologic Results from Blood Samples by Cohort and Patient
- Listing 5B: Biodistribution Endpoint Data

ADVERSE EVENT TABLE SHELL FOR TDU13600

PRIMARY SYSTEM ORGAN CLASS HLGT: High Level Group Term HLT: High Level Term Preferred Term n(%)	Cohort 1 (1.4×10^5 TU) (N=3)	Cohort 2 (4.7×10^5 TU) (N=3)	Cohort 3 (1.4×10^6 TU) (N=3)	All Cohorts (N=9)
Any Class	X (X%)	X (X%)	X (X%)	X (X%)
SOC1	X (X%)	X (X%)	X (X%)	X (X%)

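### No entry in the final table of contents gives the within-patient between-eye contrast that defines the secondary endpoint, and full-field ERG is listed for the study eye only

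*SAP*

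**What the plan says.** **The endpoint.** Protocol 6.2 assesses biological activity "through changes in function relative to the untreated contralateral eye utilizing the following retinal analytical techniques", with the 6- and 12-month visits as primary time points. SAP 5.2 repeats this. SAP 7.4 describes change from Day -28 to Weeks 24 and 48 "in function relative to the untreated, contralateral eye in several visual function measures". Protocol 4.10 explains the role of the second eye: "the contralateral non-administered eye will act as the control", together with the untreated areas of the study eye.

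**The displays.** SAP 8.3.2 states for its own outcomes: "Tables and plots will be given for the study eye as well as for the fellow eye, and labeled appropriately". For full-field ERG, SAP 7.4.2 plans tables and graphs "for study eye and fellow eye as appropriate" and adds: "Mean changes from baseline will also be summarized". SAP 8.4.2 is unconditional: "Fellow eye data will be summarized similarly".

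**The final contents list.** The memorandum replaces the SAP version 2 list of tables, listings and figures and keeps the SAP table formats except for adverse events. Its only full-field ERG entry is Listing 4L, "Full Field ERG Response (Study Eye) Amplitude and Implicit Time Data by Cohort, Patient and Visit".

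**The baseline.** SAP 7.4 uses Day -28. Protocol 6 uses the average of all pre-surgery values for BCVA and perimetry, and the last pre-surgery value for everything else. SAP 5.1 averages screening-period values for BCVA and perimetry, and SAP 7.4.1 does so for perimetry.

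**The concern.** The study is open-label and has no untreated group, so the fellow eye is the main comparator for the secondary objective. The endpoint is worded as a contrast between two eyes of one patient, but the analysis sections (SAP 7.3.2, 7.3.3, 7.3.5, 7.4.1, 7.4.2) list, plot or summarise each eye separately, and no formula for the contrast appears.

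If the final contents list is followed as written, the stated endpoint is never computed by the trial team. Each reader would derive it, possibly from different baselines, and for full-field ERG the listed output may not allow it at all.

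**Working it through.** The documents give no sample size or power calculation (Protocol 13.1, SAP 6.1), so there is no planned figure to reproduce. The check is a count, a comparison of texts and one variance ratio.

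**1. Count of entries.** Source: the contents list in the memorandum. A range such as 3T-3V counts as one entry. The eye shown is read from the title or, where the title is silent, from the SAP section 8 shell that the memorandum carries over. Entries on IOP alone (3N, 3P, 3W-3Y, 3AA) are left out because IOP is not a listed secondary endpoint.

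| Eye shown | Entries | Number |
|---|---|---|
| Both eyes, separately | 3L, 3M, 3T-3V, 3EE, 3FF-3HH, 3II-3KK, 4A, 4H, 4M, 4N, 4O | 11 |
| Study eye only | 3O, 3Q-3S, 3Z, 4I-4K, 4L | 5 |
| Eye not named | 4B-4D, 4E-4G | 2 |
| Study-eye change minus fellow-eye change | none | 0 |

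Total: 11 + 5 + 2 = 18.

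**2. What can be derived by hand.** Both eyes are available by patient for BCVA (Listing 3L), OCT (Listing 3EE), GATE (Listing 4A), SKP (Listing 4H) and multifocal ERG (Tables 4M-4O). The per-patient contrast is recoverable there.

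The BCVA summary, Table 3M, gives N, mean, SD, minimum and maximum for each eye in separate blocks. Subtracting the means gives the mean contrast but not its spread. With equal SDs s in the two eyes and between-eye correlation r, the SD of the difference is s × √(2(1 − r)). The documents give no r. Assuming r from 0 to 0.9, the SD runs from 1.41s to 0.45s.

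**3. Full-field ERG.** SAP 7.4.2 and 8.4.2 plan for fellow-eye data, and 7.4.2 for mean changes. The contents list has Listing 4L for the study eye, no fellow-eye companion and no full-field mean-change summary. SAP Table 4C already carried the study-eye title, directly below the sentence promising the fellow eye. The SAP 9 patient-profile shell for full-field ERG names no eye, whereas the OCT, perimetry and multifocal ERG shells have study and fellow columns.

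**4. Baseline.** The schedule plans three pre-surgery tests of BCVA and perimetry: one at Day -28 and two at Day -1. Let each test have independent error with SD w.

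- One baseline value: error variance of change = w²(1 + 1) = 2w².
- Mean of three: w²(1 + 1/3) = (4/3)w².
- SD ratio = √(2 ÷ (4/3)) = √1.5 = 1.22.

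The ratio is the same for the between-eye difference if the between-eye error correlation is equal at each test. It is smaller if the two Day -1 tests share error, so 22% is an upper limit. For OCT, scheduled at Day -28 and Day -1, the Day -28 rule and the last-value rule also select different measurements. For ERG they agree, because Day -28 is the only scheduled pre-surgery ERG.

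**5. Dose within cohort.** By measured strength, Cohort 3a had one patient at 0.33×10^6 and two at 2.4×10^6 TU/eye (Protocol Table 3). A by-cohort summary would pool them, whereas Protocol 13.4.3 asks for individual change plotted against dose received.

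**The case against.** **Relative to need not mean subtraction.** Protocol 13.2 and 13.4.3 prescribe descriptive summaries and individual plots, and SAP 7.0 warns that comparing non-randomised eyes could be biased. This stands as a reason for a descriptive, footnoted display. It does not withdraw the endpoint, which SAP 5.2 and 7.4 retain.

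**The data are mostly there.** This stands. A reader might infer that fellow-eye results are missing from the final analysis or that the endpoint cannot be assessed. The documents do not support that: 11 of the 18 entries show both eyes, and the SAP 9 profiles would add to them if issued. The memorandum neither lists nor withdraws the profiles.

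**The full-field ERG gap may be only a title.** This also stands. A reader might infer that fellow-eye full-field ERG was deliberately dropped, or that the contrast is certainly impossible. Neither is shown: SAP 8.4.2 is not rescinded, and the title matches SAP Table 4C. Equally, nothing clearly closes the gap. Nor is a tally of lost ERG contrasts meaningful: it would rest on that title, and entry to Cohorts 1, 2 and 3a required undetectable rod responses.

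**The average baseline is probably intended.** SAP 5.1 and 7.4.1 are specific, and a profile footnote describes an averaged BCVA. That makes the conflict easy to resolve, but SAP 7.4, the section defining the contrast, still says Day -28.

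**A median and range of three patients add little.** Agreed; individual values are better.

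**Conclusion.** The point holds as a reporting gap that should be closed. The plan names a within-patient between-eye contrast as its secondary endpoint, and 0 of 18 relevant final entries tabulate it. It can be worked out by hand for five modalities. For full-field ERG, the listed output and the SAP text disagree and need reconciling.

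The baseline conflict is worth at most a 22% larger measurement-error SD for BCVA and perimetry, assuming independent errors and three baseline tests. It says nothing about true variation between patients. The count depends on treating each range as one entry and on the SAP shells carrying over as the memorandum states. The point does not show that any result would be wrong or that data were withheld.

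**What to change.** 1. Add the fellow eye to Listing 4L, or add a companion listing, and restore the full-field ERG mean-change summary planned in SAP 7.4.2.
2. Add one descriptive table of per-patient study-eye change minus fellow-eye change at Weeks 24 and 48 for BCVA, GATE volume, SKP isopter areas, ERG amplitudes and OCT. Show individual values beside the dose received by measured strength, so that the two measured doses in Cohort 3 are not pooled. No tests.
3. State the Protocol 6 baseline in the table header: the average of all pre-surgery values for BCVA and perimetry, the last pre-surgery value otherwise. Align SAP 7.4 with it.
4. Footnote that the eyes were not randomised and that only the study eye had surgery.

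The cost is a little programming on data the SAP already plans to report. The drawback is that the contrast mixes eye selection and the effect of surgery with any vector effect, which is why the footnote is needed.

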7.4.1 Full-field Kinetic and Static Perimetry

Full-field kinetic and static perimetry will be used to document scotoma and the level of retinal function for each patient, and clinically significant changes from Day -28 will be highlighted. Perimetry will be performed three times during the screening period (once at Day -28 and twice at Day -1) and the mean of the reported perimetry values will be used to determine baseline perimetry measurements.

Individual and mean change in total volume loss in visual field as well as total volume of full hill of vision will be plotted (dB steradians) over time. Values in each eye will be listed by patient, cohort and visit.

Semi-automated kinetic perimetry (SKP) will be used to estimate total area (degrees²) of visual field sensitivity for different stimulus intensity levels (I4e, III4e and V4e isopters). Individual and mean change in total areas will be plotted against time. Values in each eye will be listed by patient, cohort and visit.

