- Laboratory test abnormalities or abnormalities in electrocardiogram or chest X-ray that, in the opinion of the principal investigator, are clinically significant and would make the patient unsuitable for participation in the study.
- Intercurrent illness or infection 28 days prior to SAR421869 administration.
- Contraindications to use of anesthesia (local or general, as appropriate).
- Concurrent anti-retroviral therapy that would inactivate the investigational agent.
- Pre-menopausal or non-surgically sterile women who are unwilling to use an effective form of contraception such as the contraceptive pill or intrauterine device.
- Pregnant or breastfeeding women.
- Males or females who do not agree to use barrier contraception as specified in the inclusion criteria.
- History of any investigational agent within 28 days prior to SAR421869 administration.
- Participation in a prior gene transfer therapy study.
- Enrolment in any other clinical study, for any condition, including those relating to Usher syndrome Type 1B, throughout the duration of the SAR421869 study.
- Current or anticipated treatment with anticoagulant therapy or the use of anticoagulation therapy within the four weeks prior to surgery.
- Long term treatment with systemic corticosteroids within 28 days prior to the screening visit or ongoing systemic corticosteroid treatment at screening or on Day -1.
- Current treatment with immunosuppressant therapies.
- A history of malignancy within a five year period or have had a positive cancer screening test within a one year period of the screening visit.
- Past medical history of HIV, or hepatitis A, B or C.
- Inability to comply with the study protocol.

Statistical Analysis

This is an exploratory study, the primary objective of which is to evaluate safety and estimation of biological activity effects. No formal sample size calculation has been performed.

Due to a small number of patients enrolled in this study, the data will be analyzed by descriptive statistics and exploratory figures. A statistical analysis plan will be finalized prior to database lock. It is envisaged that analyses will be performed on all available data.

BCVA and perimetry measurements are subject to broad intra-individual variability. The baseline value used for statistical analysis of these measures will be an average of all values obtained before surgery.

Interim Analysis

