2 STUDY SCHEDULE

2.1 FOR COHORTS 1-3A

	Pre-SAR421869		Days			Weeks					
	-28	-1	0	Day 1	1	2	4	12	24	36	48 ^k
			Surgery		±3 days	±3 days	±3 days	±14 days	±14 days	±14 days	±14 days
Visit Windows	+10 days	-7 days	N/A	N/A							
SAR421869 administration			X								
Entry Criteria	X										
Informed consent/assent	X										
Medical history	X										
Concomitant medication	X	X	X	X	X	X	X	X	X	X	X
Anesthesia assessment	X										
Height	X										
Weight	X										
Vital signs ^c	X	X	X	X	X	X	X	X	X	X	X
ECG	X ^o										
Chest X-ray	X ^o										
Physical examination	X										X
Ophthalmological examination											
BCVA ^a	X	X		X	X	X	X	X	X	X	X
Slit lamp examination	X	X		X	X	X	X	X	X	X	X
Intraocular pressure	X	X		X	X	X	X	X	X	X	X
Fundoscopy	X	X		X	X	X	X	X	X	X	X
Autofluorescence	X						X	X	X	X	X
OCT ^p	X	X		X	X	X	X	X	X	X	X
Perimetry (SKP, GATE, microperimetry) ^a	X ^m	X ⁿ				X	X	X	X	X	X
Fundus photography ^b	X		X	X		X	X		X	X	X
Multifocal and full Field ERG	X								X		X
VFQ-25		X ^o									X ^o
Hematology ^d	X	X ^o		X ^o			X ^o		X ^o		X ^o
Chemistry panel ^e	X	X ^o		X ^o			X ^o		X ^o		X ^o
Kidney function ^f	X	X ^o					X ^o		X ^o		X ^o
Liver function ^g	X	X ^o		X ^o			X ^o		X ^o		X ^o
Coagulation ^h	X	X ^o									

Visit Windows	Pre-SAR421869			Days										Weeks					
	-28	-1	0 Surgery	Day 1	1		2		4		12		24		36		48 ^k		
					±3 days	±3 days	±3 days	±14 days	±14 days	±14 days	±14 days	±14 days	±14 days	±14 days	±14 days	±14 days	±14 days		
Visit Windows	+10 days	-7 days	N/A	N/A															
Urinalysis ⁱ	X	X ^o			X ^o					X ^o			X ^o				X ^o		
Blood for PCR	X			X ^j	X	X	X	X	X	X	X	X	X	X	X	X	X	X	
Blood for Immunology			X ^o							X	X	X	X	X	X ^q	X ^q			
Urine for PCR	X			X ^j	X	X	X	X	X	X	X	X	X	X	X	X	X	X	
Urine pregnancy test	X ^o	X ^{o,l}								X ^o	X ^o								
Adverse events	X	X	X	X	X	X	X	X	X	X	X	X	X	X	X	X	X	X	

Notes:

- a. BCVA, Semi-automated Kinetic Perimetry (SKP), full field German Adaptive Thresholding Estimation (GATE) static perimetry and microperimetry will be performed 3 times during screening period; once at the screening visit (Day -28) and on two occasions at baseline (Day -1).
- b. A photomontage will be taken at the screening visit and Week 48 only.
- c. Vital signs: blood pressure (BP, lying down), heart rate (HR) and temperature taken and recorded before SAR421869 administration. Following surgery vital signs will be measured every 30 minutes for one hour. Vital signs will be obtained on all subsequent follow-up visits.

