7.3 Primary Endpoint

The primary endpoint is composed of several endpoints related to safety, each of which will be presented at the patient and eye level (refer to [Sections 8](#) and [9](#)). Primary analysis for these endpoints, except adverse events, will compare change from Day -28 to Week 48. Graphical presentation of cohort summaries will also be presented as described, and clinically important changes from Baseline (Day -28) to Week 48 will be indicated and summarized.

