7.3.2 Best-Corrected Visual Acuity (BCVA)

BCVA (Early Treatment Diabetic Retinopathy Study [ETDRS] letters read) will be listed by visit and eye. BCVA for all patients' study eye and fellow eye will be presented graphically by visit and cohort. Mean changes in BCVA by visit and cohort will be summarized in a table and graph by cohort and visit.

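### SAP 7.4.1 and 7.3 flag perimetry and BCVA changes from the single Day -28 test without a numeric limit, against the averaged baseline the SAP itself adopts

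*SAP*

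**What the plan says.** For perimetry, SAP 7.4.1 states that "clinically significant changes from Day -28 will be highlighted". It gives no size of change for GATE volume or SKP area. Its next sentence takes the mean of three screening tests, one at Day -28 and two at Day -1, as the perimetry baseline.

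For the primary endpoints, BCVA among them, SAP 7.3 states that "clinically important changes from Baseline (Day -28) to Week 48 will be indicated and summarized". SAP 7.3.2 adds no letter limit: "Mean changes in BCVA by visit and cohort will be summarized in a table and graph by cohort and visit". The list of final outputs in the memo of 30 August 2019, attached to the SAP, adds Table 3O, titled "Patients Experiencing BCVA Change in the Study Eye at Week 48 Following Treatment by Cohort".

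SAP 5.1 heads its list of safety assessments with a Day -28 baseline, then makes the screening average the baseline for BCVA and perimetry. The protocol gives the reason for averaging in its synopsis: "BCVA and perimetry measurements are subject to broad intra-individual variability". The repeats are scheduled in Protocol 2.1, note a: "BCVA, Semi-automated Kinetic Perimetry (SKP), full field German Adaptive Thresholding Estimation (GATE) static perimetry and microperimetry will be performed 3 times during screening period".

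Other measures do have stated rules: at least two steps for inflammation (SAP 7.3.3), pressure bands (7.3.4), laboratory thresholds (7.3.6), normal to abnormal for physical examination (7.3.9) and a fall of more than 50% for ERG (7.4.2).

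**The concern.** The two measures singled out as variable are the two functional measures whose flags have no stated size, and the flags point to one test when the plan has already chosen an average to dampen noise. A flag from Day -28 and a change from the averaged baseline can disagree for the same eye at the same visit.

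With three patients per cohort in the adverse event shell of the 2019 memo, one or two highlighted eyes can be read as harm or as activity. Without a stated limit, a reader of the report cannot tell how many highlights to expect from test noise alone. The repeats that would answer this are collected, but the plan uses them only to form an average.

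**Working it through.** The plan states no limit, test-retest SD or sample-size calculation, so there is no figure to reproduce. Results are in units of s, the within-eye SD of one test.

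**Inputs.** Three pre-surgery tests (SAP 7.4.1; Protocol 2.1, note a). Nine patients in three cohorts of three (shell in the 2019 memo). Both eyes reported (SAP 7.0). Assumed: normal, independent errors, no true change and no learning effect.

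**Step 1: noise in a change.**
- Against the mean of m tests, SD = s × sqrt(1 + 1/m). For m = 3 this is 1.155s; for m = 1 (Day -28 alone) it is 1.414s.
- The two-sided 95% limits, with s known, are 1.96 × 1.155s = 2.26s and 1.96 × 1.414s = 2.77s. For m = 2 the limit is 2.40s.

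**Step 2: effect of the reference.** The chance that an unchanged eye is flagged at one visit is 2 × [1 − Φ(cut/SD)]. For nine eyes, the expected number is 9p and the chance of at least one is 1 − (1 − p)^9.

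| Cut | Reference | Per eye | Expected of 9 | At least one of 9 |
|---|---|---|---|---|
| 1.5s | Day -28 | 29% | 2.6 | 95% |
| 1.5s | mean of 3 | 19% | 1.7 | 86% |
| 2s | Day -28 | 16% | 1.4 | 79% |
| 2s | mean of 3 | 8% | 0.75 | 54% |
| 2.26s | Day -28 | 11% | 1.0 | 65% |
| 2.26s | mean of 3 | 5% | 0.45 | 37% |

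The cuts are illustrations; the plan names none. At any given cut, Day -28 gives more noise flags than the average.

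**Step 3: can the repeats supply s?** Three tests give 2 degrees of freedom per eye.
- One eye: 2 df. The 95% range for s is a factor of 0.52 to 6.28, which is unusable.
- Nine study eyes: 18 df, 0.76 to 1.48.
- Eighteen eyes: 9 × 2 × 2 = 36 df, sqrt(36/χ²) = 0.81 to 1.30, treating the two eyes as independent.

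Because s is estimated, t replaces 1.96. At 36 df, 2.028 × 1.155 = 2.34s.

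**Step 4: does the rule hold its rate?** Simulation with 18 eyes:

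| Variance shared within a visit (assumed) | 2.26 × estimated s | 2.34 × estimated s |
|---|---|---|
| none | about 5.7% | 5.0% |
| 25% | 7.5% | 6.5% |
| 50% | about 9.5% | 8.5% |

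The rate rises because two of the three tests belong to the Day -1 visit and share that visit's error.

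**Step 5: the protocol's 15-letter limit.** Against the mean of three tests, the chance that noise alone gives a fall of more than 15 letters is 1 − Φ(15/(1.155s)). For an assumed s of 3, 5 and 8 letters this is below 0.001%, 0.5% and 5.2% per eye per visit.

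**The case against.** **BCVA loss already has a limit.** A reader might infer that the plan has no numeric rule at all for BCVA harm. That is not so. Protocol 11.5 makes an adverse event of special interest of any event causing a fall of more than 15 letters, or more than 0.3 logMAR, that lasts over a week or two successive visits. SAP 7.3.1 summarizes such events as the protocol details them, and the memo keeps those tables. Step 5 shows that this limit screens out most noise unless s is large. It applies to events that cause a loss, is not tied to the SAP 7.3 flag, and covers neither gains nor perimetry.

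**Day -28 may be only a label.** Table 3M uses pre-surgical BCVA, and a patient-profile footnote averages the two screening visits. This suggests that averaging is intended, but SAP 7.3 and 7.4.1 still say otherwise.

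**High false-flag rates are hypothetical.** A reader might infer that most stable eyes will be flagged. That needs a low cut such as 1.0s or 1.5s, which no document proposes. The memo shows perimetry only in listings and figures, and Table 3O concerns Week 48 alone, so a six-visit rate does not describe a planned count.

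**Who sets the flags.** The study is open-label, but no passage says who will judge the changes. A charge that unmasked staff will choose limits after seeing results is not supported.

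**Table 3O.** Only its title is shown. The Table 3P title also omits its pressure bands, which SAP 7.3.4 defines. Missing categories in a title prove little alone; the point is that SAP 7.3.2 defines none either.

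**A noise limit is not clinical importance.** This stands. If s is large, the limit could leave a real loss unmarked, so it must not carry the clinical label or replace the listings.

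**Conclusion.** The reference test and the missing limit are genuine defects. The contradiction with the averaged baseline is plain on the text and is the firmer part. The missing limit holds in full for perimetry. For BCVA it holds for gains and for the SAP 7.3 flag, but not for sustained losses of more than 15 letters.

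At a 2.26s cut, using Day -28 instead of the three-test mean roughly doubles the noise flags, from 5% to 11% per eye per visit. This rests on normal, independent errors and no learning effect; the absolute number of flags cannot be stated without s.

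The practical impact is modest: no formal tests are planned, and values for both eyes are listed. The change is still worth making before lock, because the SAP promises highlights and the data for a rule already exist.

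**What to change.** Before database lock, in SAP 7.3, 7.3.2 and 7.4.1:

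1. For BCVA and perimetry, replace Day -28 with the mean of all pre-surgery tests.
2. For GATE volume, SKP area per isopter and BCVA, estimate s from the pre-surgery repeats, pooled over treated patients. Compare study and fellow eyes before pooling them, since the fellow eye has no field criterion. Mark a change as beyond test-retest variability when it exceeds t × s × sqrt(1 + 1/m), with m that eye's number of baseline tests and t on the pooled degrees of freedom. Protocol 9.3.4 allows as few as two perimetry tests, so m must not be fixed at 3 and 36 df is a best case for nine patients. State that same-visit repeats may understate visit-to-visit noise.
3. Call a change confirmed if it is also present at an adjacent scheduled visit; for Week 48, the preceding one, since no later visit exists.
4. Apply the same rule to the fellow eye. Table 3O covers the study eye only, so this needs one added output.
5. Define Table 3O by letter categories that include the protocol's loss of more than 15 letters. Keep the sustained event separate, since its duration condition makes its count different. List all values, flagged or not.

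The cost is a short SAP addition, one derivation and one output, with no new data. The limit is itself estimated: at 36 df, s is known to within about −19% to +30%.
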